## 2. Objective

Our long term objective is to improve the lives of veterans and civilians with impaired upper extremity (UE) function after stroke. We previously developed a novel training protocol that combined the ARMin and HandSOME exoskeletons (Fig. 1). This is one of only a few arm exoskeletons that allow coordinated whole limb training in reach and grasp tasks with both virtual and real objects. A pilot clinical trial using this robotic device with stroke subjects was funded by the Department of Veterans Affairs and performed at the DC VAMC under protocol# 01103: "Use of an innovative robotic system for upper limb rehabilitation following stroke". We found that this robotic exoskeleton elicited improvements in arm function that can potentially supplement conventional methods to improve outcomes (Brokaw 2014). In this study, a clinical trial will be performed to evaluate this robotic therapy against conventional treatment.

**Figure 1.** (A & B) ARMin and HandSOME devices. (C) Visual feedback user interface during the shelf task. Virtual cups are grasped and placed on a high shelf. Arrows indicate the direction of joint rotation needed to complete the task. The arrow colors indicate if a joint is not rotating in the correct direction and preventing advancement in the trajectory. During training with real objects, the subjects focus on the object to be moved and refer to the visual interface only when they get stuck and need guidance.

## 3. Aims / Hypotheses

Specific AIM: We will perform a clinical trial to compare the effectiveness of robotic training to conventional therapy from an occupational therapist. To take advantage of the facilitatory effect of robot therapy on subsequent conventional therapy, the experimental treatment will be 12 hours of robot therapy followed by 12 hours of conventional therapy. Chronic stroke

subjects (N=46) will be randomly assigned to receive this experimental treatment or 24 hours of conventional therapy from an occupational therapist.

**Hypothesis I:** Gains from the initial 12 hours of robotic therapy will be significant ( $p < 0.05$ ) in the domains of impairment (Fugl-Meyer), function (Action Research Arm Test) and amount of arm use (Motor Activity Log).

**Hypothesis II:** Gains in impairment, function and arm use in the experimental group (robot + conventional therapy) will be significant ( $p < 0.05$ ) and clinically important (defined as greater than 10% gain) immediately after all treatments and also at the 6-month follow-up.

**Hypothesis III:** Gains in impairment, function and arm use will be significantly greater in the experimental group (robot + conventional therapy) than the conventional therapy control group immediately after the end of all treatments and also at the 6-month follow-up.

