### Data analysis

Prior to conducting the main analyses, summary statistics, histograms, and scatter plots will be inspected to verify that distribution assumptions are met. Adjustments (e.g., transformations) to the main dependent measures will be made as necessary to address any problems (e.g., skewness, outliers) that these preliminary analyses uncover. To test Hypotheses, a series of mixed model ANOVAs will be tested, one for each dependent variable, with the within-subject variable being timepoint (pre, after 12 hours of treatment, after 24 hours of treatment, 6 month followup) and the between-subject variable of group (experimental vs. control). A significant effect of timepoint or a significant timepoint x group interaction would be followed with a series of paired t-tests, with Bonferoni corrections. Hypothesis I will be tested with a paired t-test between the pre and post-robotic timepoint (after 12 hours of robotic treatment). Hypothesis II will be tested with a paired t-test between the pre and post-treatment timepoint in the experimental group (after 12 hours of robot and 12 hours of conventional therapy). Additionally a z-test will be performed for the hypothesis that the proportion of subjects with 10% or greater gain at the post-treatment timepoint is significantly greater than zero. A final paired t-test and z-test between pre and 6-month followup timepoints will be performed. If a change is statistically significant, mean changes will be compared to predetermined MCID values of 10% of full scale. To test Hypothesis III, the timepoint x group interaction effect will be examined in the mixed model ANOVA. If significant, gains in the dependent variables will be calculated at the post-treatment and 6-month timepoints (relative to the pre timepoint), and between-group differences will be tested with unpaired t-tests, with Bonferoni corrections.

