### Power Analysis

The power analysis was based on data from our previous pilot study (Brokaw 2014). To address Hypothesis I, we calculated power to detect significant gains after only the robotic training. Using the pre-post changes after the initial period of robotic therapy from our pilot study, the effect size for the ARAT was  $d_z=1.2$ , with pre-post correlation  $r=0.94$ . In order to detect an effect this large, when using a 1-tailed paired t-test with  $\alpha=.05$ , a sample size of **N=8** is required for power > 0.90 (Faul 2009). For the Fugl-Meyer, the effect size was  $d_z=0.74$ , with pre-post correlation  $r=0.85$ , which would require a sample size of **N=18** for power > 0.90.

To power Hypothesis II, the pre-post effect size for gains on the ARAT after the experimental treatment (12 hours of robot + 12 hours of conventional therapy) was  $d_z=0.77$ , with pre-post correlation  $r=0.95$  (only using data from subjects who received robotic therapy followed by conventional therapy). In order to detect an effect this large, when using a 1-tailed paired t-test with  $\alpha=.05$ , a sample size of **N=16** is required for power > 0.90. For the Fugl-Meyer, the pre-post effect size was  $d_z=1.41$ , with pre-post correlation  $r=0.91$ . In order to detect this difference, only **N=6** subjects are required for power > 0.90.

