To address Hypothesis III, we calculated the power to detect the expected differences in gains between the experimental and control groups. The experimental treatment in our pilot study produced gains of 7 (sd=4.9) in the Fugl-Meyer. A recent study reported gains of 2.47 (sd=1.67) on the Fugl-Meyer after 24 hours of conventional therapy in 35 stroke subjects with similar intake Fugl-Meyer scores as in our pilot study (FM = 22.4 vs. 21) (Klamroth-Marganska 2014). Using these data, the mean difference in treatments will have an effect size of 1.9. For a 1-tailed unpaired t-test, **N=5** subjects in each treatment group are needed to detect this difference with power > 0.80. Similarly for the ARAT, we had gains of 5.6 (sd=4.7) after the experimental treatment in our pilot study. A different study (Fleming 2015) reported gains of 1.0 (sd=5.7) after 24 hours of conventional therapy in 17 chronic stroke subjects with similar intake ARAT scores as in our pilot study (ARAT = 26.6 vs. 20.9). Using these data, the mean difference in treatments will have an effect size of 0.84. For a 1-tailed unpaired t-test, **N=19** subjects in each treatment group will detect this difference with power > 0.80.

Therefore with **N=19** subjects in each treatment group, we will detect the anticipated pre-post changes and group differences in the ARAT and Fugl-Meyer. We had a dropout rate of 0.167 in the pilot study. Therefore, we will plan for this and recruit 23 subjects into each treatment group. We have no pilot data on the MAL to perform a power analysis for the outcome.

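### Hypothesis III claims superiority at both timepoints, but the analysis plan does not say whether one or both must be significant, applies a Bonferroni correction that a joint claim does not need, and powers only one uncorrected test

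*Combined protocol and SAP*

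**What the plan says.** **Section 3 (Aims / Hypotheses).** Hypothesis III begins "Gains in impairment, function and arm use will be significantly greater in the experimental group" and ends "than the conventional therapy control group immediately after the end of all treatments and also at the 6-month follow-up". The two timepoints are joined, so the hypothesis as written is true only if the advantage exists at both.

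**Section 5, Data analysis.** The first step is an omnibus test: "To test Hypothesis III, the timepoint x group interaction effect will be examined in the mixed model ANOVA". There is one model per outcome, over four timepoints. Only if the interaction is significant are gains from baseline compared at the end of treatment and at 6 months, where "between-group differences will be tested with unpaired t-tests, with Bonferoni corrections". No sentence says what pattern of results supports Hypothesis III. No sentence says whether the correction divides alpha by two (timepoints), by six (two timepoints for three outcomes) or by another number.

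**Section 5, Power Analysis.** The ARAT comparison sets the sample size: "For a 1-tailed unpaired t-test, N=19 subjects in each treatment group will detect this difference with power > 0.80". This is one comparison with no correction. The Fugl-Meyer comparison needs only 5 per group by the plan's own figures, and the MAL has no power calculation.

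**The concern.** Three parts of the plan should describe the same decision, and they do not meet. The hypothesis is a conjunction. The analysis applies a correction whose usual purpose is to permit a claim when at least one test succeeds. The sample size is for a single test.

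Two things are at stake. First, the reading of a split result is left until the data are known. A benefit present at the end of therapy and gone by 6 months is a plausible outcome, and the 6-month visit is there to detect it. Second, if the joint claim is kept, dividing alpha between the timepoints makes it harder to establish without lowering an error rate that needed lowering, and the stated power does not describe the claim.

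**Working it through.** **Inputs from the Power Analysis section.** ARAT gains of 5.6 (SD 4.7) and 1.0 (SD 5.7, n = 17); d = 0.84; 19 per group; 1-tailed. The alpha of 0.05 is stated there for the paired tests and is taken to apply here as well.

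**Assumptions, not in the documents.** The same d = 0.84 at 6 months; correlation between the two gains from 0 to 0.9; a Bonferroni family of two; a pilot n of 6 for the 5.6 gain (used only to reproduce d).

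**Step 1: reproduce the plan's figure.** Pooled SD = √[(5 × 4.7² + 16 × 5.7²)/21] = √(630.29/21) = 5.48, so d = (5.6 − 1.0)/5.48 = 0.84. Noncentrality = 0.84 × √(19/2) = 2.59 on 36 df. Power at 1-tailed 0.05 is 0.815. The plan's 19 per group is correct for one uncorrected test.

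**Step 2: one test at the corrected level.** At 1-tailed 0.025 the power is 0.712, and 24 per group would be needed for 0.80. If the family were six (0.05/6), the power is 0.537 and 32 per group would be needed.

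**Step 3: does a both-required claim need the correction?** If the claim is false, at least one timepoint has no effect. Then P(both significant) ≤ P(the null timepoint is significant) ≤ alpha. Simulation (200,000 pairs of t statistics) agrees at 1-tailed 0.05 uncorrected: a very large effect at one timepoint and none at the other gives 0.050; no effect at either gives 0.0025 to 0.031. By contrast, a claim resting on either timepoint has error 0.068 to 0.098 uncorrected and 0.035 to 0.050 with Bonferroni. The correction therefore suits an either-timepoint claim and is unnecessary for a joint one.

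**Step 4: joint power, 19 per group, d = 0.84 at both timepoints, interaction test ignored.**

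| Correlation of gains | Both at 0.05 | Both at 0.025 | Loss | Exactly one significant at 0.025 |
|---|---|---|---|---|
| 0 | 0.663 | 0.507 | 0.156 | 0.41 |
| 0.5 | 0.707 | 0.570 | 0.137 | 0.29 |
| 0.7 | 0.730 | 0.602 | 0.128 | 0.22 |
| 0.9 | 0.765 | 0.648 | 0.117 | 0.13 |

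The first row can be checked by hand: 0.815² = 0.66 and 0.712² = 0.51. The last column shows how often a truly sustained effect would give a split result that the plan does not say how to read.

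**Step 5: sample size for joint power of 0.80.** 25 down to 21 completers per group uncorrected, and 31 down to 26 with Bonferroni, as the correlation goes from 0 to 0.9.

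**Step 6: add the interaction test.** With the four-timepoint F-test at 0.05 required first, correlation 0.5 to 0.7 and an assumed 12-hour effect between 0 and 0.84, uncorrected joint power is about 0.62 to 0.73, and the loss from Bonferroni is about 8 to 12 points.

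**The case against.** A reader might infer that the plan contains two conflicting success rules, so that the same data would confirm Hypothesis III under the analysis section and refute it under Section 3. The documents do not support that. The analysis section states no success rule at all, and it nowhere says that one significant timepoint is enough. Section 3 is the only text that says what Hypothesis III asserts. The defect is an unstated decision rule with a correction that does not match the claim, not a contradiction between two rules.

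A reader might also infer that the correction protects nothing. That goes too far. It protects separate statements about each timepoint, whose combined error would otherwise reach 0.068 to 0.098 when neither effect exists. Any such statements still need either the correction or a descriptive label.

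Three further objections stand in part:

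- The interaction test comes first and filters some results. But it asks only whether the group profiles differ somewhere over four visits, so it cannot settle whether one or both later timepoints must differ.
- The 6-month effect, the correlation and the family of two are not in the documents. The direction of the result does not depend on them: joint power cannot exceed the single-test power of 0.815, and falls below it unless the two tests always agree.
- Section 3 also joins the three outcomes with a conjunction, and Hypothesis II has the same two-timepoint wording. Treating outcomes separately follows the plan's one-model-per-outcome analysis, but the plan should say so.

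**Conclusion.** The point holds as a mismatch between claim, analysis and power. For the both-timepoints claim as worded:

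- A correction across timepoints is not needed. It costs about 12 to 16 points of joint power at 1-tailed 0.05 with the interaction test ignored, and about 8 to 12 points with it included under the assumptions in step 6.
- Power above 0.80 with 19 per group does not apply. Joint ARAT power is about 0.66 to 0.77 uncorrected and 0.51 to 0.65 with Bonferroni over two tests, and somewhat lower once the interaction test is included.

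Dropping the correction narrows the shortfall but does not close it. These figures rest on d = 0.84 at both timepoints, a correlation of 0 to 0.9 and 1-tailed tests. With two-sided tests at 0.05, counted in the favourable direction, the uncorrected joint power falls to the 0.025 column. The value d = 0.84 is taken as given, although Background reports the 5.6-point ARAT gain as following the first robot period only. That figure should be reconciled before power is restated.

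**What to change.** In the Hypothesis III part of Data analysis, state: *For each outcome, and after a significant timepoint by group interaction, Hypothesis III is supported only if the group difference in gain is significant at both the end of treatment and 6 months, each tested at the full alpha with no correction across the two timepoints. A difference at one timepoint only is reported as descriptive, or at the Bonferroni-corrected level, and does not confirm Hypothesis III.* State the sidedness, and say whether any correction applies across the three outcomes.

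In Power Analysis, restate the ARAT power for this rule, giving the assumed 6-month effect and correlation and allowing for the interaction test.

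If two separate claims were intended, reword Hypothesis III as two claims, keep Bonferroni with its number of tests stated, and give power at the corrected alpha: about 0.71 per timepoint at 1-tailed 0.025 if the family is two.

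The change needs no new visits or data. The cost is a less favourable power figure. The sponsor must either accept it or plan for 21 to 25 completers per group (42 to 50 in total, against 38), before allowing for the interaction test. An advantage at the end of treatment alone would not confirm Hypothesis III, which is what Section 3 already implies.

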#### **4. Background**

Approximately 795,000 individuals in the United States have a stroke each year (Go 2014). Approximately 15,000 veterans are hospitalized for stroke each year (<http://www.queri.research.va.gov/str/>), with costs of \$75 million for post-acute inpatient care and \$88 million annually for follow-up care ([http://www.queri.research.va.gov/about/factsheets/stroke\\_factsheet.pdf](http://www.queri.research.va.gov/about/factsheets/stroke_factsheet.pdf)). Fifty percent of stroke survivors older than 64 have persistent hemiparesis at six months post-stroke and 26% are dependent in activities of daily living (ADL) (Roger 2012). In the upper extremity, reaching and grasping movements are often impaired and a focus of rehabilitation. Impairments include decreased muscle activation and weakness (Zackowsky 2004, Gowland 1992), disrupted interjoint coordination (Cirstea 2003, Beer 2000), decreased smoothness of movement (Rohrer 2002, Krebs 1999), and dyscoordination between reach and grasp movements (van Vliet 2007). Limitations in ADL ability and decreased quality of life can result from even mild impairments in upper-limb function (Nichols-Larsen 2005, [name] 2006).

In a pilot clinical trial funded by the Department of Veterans affairs, we found that the robotic exoskeleton elicited improvements in arm function that can potentially supplement conventional methods to improve outcomes (Brokaw 2014). The robot has 5 active motors that assist with 3 shoulder DOF, elbow flexion/extension and supination/pronation (Fig. 1). A passive hand orthosis (HandSOME) is worn to assist with opening the hand. Twelve chronic stroke subjects were randomized to 12 hours of robotic or conventional therapy and then crossed over to the other therapy type after a 1 month washout period. Across the 3 month study period, subjects showed significant improvements in the Fugl-Meyer Test of Motor Function ( $p = 0.013$ ) and Box and Blocks tests ( $p = 0.028$ ). The Fugl-Meyer (Fugl-Meyer 1975) tests impairment throughout the upper extremity, while the Box and Blocks (Platz 2005) scores the number of one-inch blocks that can be moved from one box to another over a partition in one minute. In the Action Research Arm Test (ARAT, Lang 2006), a measure of function, the robotic intervention produced significantly greater improvements than conventional therapy ( $p = 0.033$ ).

Interestingly the robotic training appeared to facilitate the effects of conventional therapy. There were significant gains in the Box and Blocks after conventional therapy only if it was preceded by a period of robotic training ( $p = 0.044$ ). Clinically significant gains were present in the Fugl-Meyer when robot therapy was given first and followed by conventional therapy. The mean gain was  $7 \pm 2.2$  points, which was statistically significant ( $p = 0.034$ ). This gain was larger than 10% of full scale (6.6 points), which is considered the minimally clinically important difference (MCID) on this scale (Gladstone 2002, Lo 2010, Page 2012). In the ARAT, the gains at the end of treatment (robot + conventional) did not reach the MCID threshold of 10% or 5.7

points (van der Lee 1999, van der Lee 2001). However, gains following the first period of robot treatment did approach the MCID threshold (gain=5.6±2.1; p=.057).

## **5. Study Design**

### **Overview**

The robotic system will be used in a clinical trial with chronic stroke subjects with impaired upper extremity function. 46 subjects will be randomly assigned to an experimental or control group. The experimental group will receive 1-hour robotic training sessions, 3 times per week for a total of 12 sessions supervised by a research assistant. Immediately following this robot training, these subjects will receive the same dosage and schedule (1-hour sessions, 3 times/week, 12 total sessions) of conventional one-on-one therapy from an occupational therapist. The control group will receive 24 hours of conventional one-on-one therapy on the same schedule (1-hour sessions, 3 times/week). Clinical and biomechanical evaluations will be performed before treatment, after 12 hours of treatment, after 24 hours of treatment and at a 6-month follow-up.

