### **Recruitment**

Subjects will be recruited from the outpatient clinics at the Washington DC VAMC. The DC VAMC annually has over 100 admissions for stroke. [name], has WOC status at the DC VAMC and will confirm that patients meet study criteria. Additionally, veterans will be recruited from nearby MedStar National Rehabilitation Hospital (NRH), Washington Hospital Center (WHC), and Medstar Health outpatient clinics.

The inclusion criteria are: 1) Age 21 or older; 2) ischemic or hemorrhagic stroke (with confirmatory neuroimaging) that occurred more than 6 months before entering the study; 3) presence of voluntary hand activity indicated by a score of at least 1 on the finger mass extension/grasp release item of the Fugl-Meyer Test of Motor Function; 4) adequate cognitive status, as determined by Mini-Mental Status Examination (Bleeker 1988) score >24; 5) no upper extremity injury or conditions that limited use prior to the stroke. Subjects will be excluded if they: 1) cannot give informed consent; 2) have clinically significant fluctuations in mental status within a month of enrollment; 3) were not independent prior to the stroke as measured by scores <95 on the Barthel Index (de Morton 2008) or >1 on the Modified Rankin Scale (Quinn 2009); 4) have hemispatial neglect as determined by >3 errors on the Star Cancellation Test (Manly 2009); 5) have severe sensory loss as determined by a score of 2 on the sensory item of the NIHSS (Lai 1988); 6) receiving oral or injected antispasticity medications during study treatment; 7) pain that interferes with daily activities; 8) history of prior stroke.

In a previous study in chronic stroke, we found that the dropout rate was 16.7%, so we will plan to **recruit 46 subjects**. Subjects who drop out of the study will be replaced until a total of **38 subjects complete the protocols**. All therapy will be in addition to the regular PT and OT subjects may be receiving as part of their outpatient treatment. The amount of outside PT or OT targeting arm or hand function received by subjects while enrolled in the study will be logged and used as a potential covariate in the analysis.

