#### Clinical evaluations

Clinical evaluations will be performed before training, after 12 hours of treatment, after 24 hours of treatment and again at the 6-month followup. All clinical testing will be performed by an Occupational or Physical Therapist (TBN), who has extensive experience in performing these tests. He/she will be blinded to the study design and unaware of the sequence or content of training that subjects receive. The Fugl-Meyer Test of Motor Function will be used to assess motor impairments at the shoulder, elbow, wrist and fingers (Fugl-Meyer 1975). The Fugl-Meyer test scores reflexes and the ability to perform several movements and tasks on a 3-point scale. The Fugl-Meyer was designed for the recovery patterns observed after stroke and is very responsive to change in severe and moderately impaired subjects, but is less responsive in mildly impaired subjects (van der Lee 2001). The Action Research Arm Test (ARAT) (Lang 2006) is an impairment level measurement tool that assesses the functional limitations of the upper extremities. It is one of the most frequently used primary endpoints in UE training trials in stroke. The assessment incorporates 19 items that are divided into four subscales: Grasp, Grip, Pinch, and Gross movement. Item scores are summed to form a subtest score, and then a full-scale score. The ARAT has established reliability, responsiveness and validity in stroke subjects (Platz 2005). The Motor Activity Log (MAL) will be used to assess use of the limb at home (Uswatte 2006). It is a structured interview during which respondents are asked to rate how they use their more-impaired arm for 28 ADL in the home over a specified period. The MAL is administered independently to the patient and an informant. Activities include brushing teeth, buttoning a shirt or blouse, and eating with a fork or spoon. For each item the participant must report how well (6-point, Quality of Movement or QOM scale) and how often (6-point, Amount of Use scale) each activity was performed during a specified period. The MAL has high internal consistency, test-retest reliability, and high convergent validity (Uswatte 2005).

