In secondary analysis, we will look to identify the characteristics of patients who are most responsive to the treatment. Potential predictors include initial impairment level, and time-varying predictors such as amount of home use (MAL) at the previous assessment. The subjects will be divided into severe (Fugl-Meyer<30), moderate (30<Fugl-Meyer<50) and mild impairment groups (Fugl-Meyer>50). This division is based on a previous study that reported subjects with initially moderate impairment (Fugl-Meyer = 40) benefited the most from robotic therapy, with reduced effectiveness in severe and mildly impaired subjects (Hsieh 2012). The dependent variables will be gain in the FM, ARAT and MAL at each timepoint. A fixed effects (mixed) model will be used to determine if the gains over time were the same across the 3 impairment groups, and whether use at home in the preceding time interval predicts later improvement.

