## **13. Study Population**

No gender and/or ethnicity will be excluded from participating in the study. The study will attempt to maintain a balanced cohort based on both gender and ethnicity.

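### Baseline Fugl-Meyer, which the plan treats as a potential predictor of response, is neither balanced at assignment nor adjusted for in the Hypothesis III comparison of gains

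*Combined protocol and SAP*

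**What the plan says.** All references are to the combined protocol and SAP.

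- **Assignment.** Section 5, Overview: "46 subjects will be randomly assigned to an experimental or control group". Section 3 repeats this. The available design and analysis text describes no stratification, blocking or minimisation.
- **Balance.** Section 13: "The study will attempt to maintain a balanced cohort based on both gender and ethnicity". This concerns the make-up of the cohort, not severity between arms.
- **Impairment and response.** Section 5, Data analysis (secondary analysis): "Potential predictors include initial impairment level, and time-varying predictors such as amount of home use (MAL) at the previous assessment". The severe, moderate and mild Fugl-Meyer classes are justified by an earlier study in which moderately impaired subjects "benefited the most from robotic therapy, with reduced effectiveness in severe and mildly impaired subjects".
- **Hypothesis III.** The mixed model has timepoint and group as its only factors. If their interaction is significant, gains from the pre timepoint are compared: "between-group differences will be tested with unpaired t-tests, with Bonferoni corrections".
- **Covariates.** The only one named is outside PT or OT for the arm or hand, which "will be logged and used as a potential covariate in the analysis" (Recruitment).
- **Timing of the score.** "Clinical evaluations will be performed before training, after 12 hours of treatment, after 24 hours of treatment and again at the 6-month followup" (Clinical evaluations). Inclusion criterion 3 uses a single Fugl-Meyer item, not the total.

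**The concern.** The plan has a reason to expect gains to vary with initial impairment, and it measures impairment before treatment, but it uses that information only in a secondary analysis. Subtracting the pre score to form a gain removes the baseline level. It does not remove any relation between baseline and gain. If such a relation exists, a chance difference in severity between two arms of 19 to 23 subjects carries into the difference in gains that decides Hypothesis III, and nothing in the allocation or the analysis counters it. At stake are the precision of that comparison and how far readers will trust it if the baseline table shows unequal arms.

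**Working it through.** **1. The plan's sample size (Power Analysis).** ARAT gains are 5.6 (SD 4.7) experimental and 1.0 (SD 5.7, n = 17) control. Taking 6 pilot subjects in the experimental sequence (assumption: half of 12):

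- pooled SD = sqrt[(5 x 4.7² + 16 x 5.7²)/21] = 5.48
- d = 4.6/5.48 = 0.84, as stated

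A one-tailed unpaired t-test at 0.05 (noncentral t) has power 0.795 at 18 per arm and 0.815 at 19. Then 19/(1 - 0.167) = 22.8, so 23 per arm and 46 in all. The plan's figures reproduce.

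**2. How often the arms differ at baseline.** The documents give no baseline SD. Two assumed distributions, both truncated to 5-66, give a range:

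- *Plan-based:* mean 21.7 (midpoint of the quoted intake scores 21 and 22.4) and SD 4.9/sqrt[2(1 - 0.91)] = 11.5, which assumes equal pre and post SDs. After truncation the mean and SD are about 23.4 and 10.0.
- *Wider sample (assumed):* mean 30, SD 14. After truncation, about 31.0 and 12.6.

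The SD of the difference in arm means is SD x sqrt(2/23) = SD x 0.295, and P(|difference| ≥ 5) = 2[1 - Φ(5/SD of difference)]:

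- 10.0 x 0.295 = 2.95, giving 9%
- 12.6 x 0.295 = 3.72, giving 18%

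Simulation of 20,000 allocations agrees:

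| | Unstratified | Two strata (<30, ≥30) |
|---|---|---|
| Mean difference ≥ 5 points | 9-18% | 1-2% |
| Count at ≥ 30 differs by 5 or more | 13-18% | 0% |

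On a scale-free basis, an imbalance of at least 0.5 SD has probability 2[1 - Φ(0.5/sqrt(2/n))]: 9% at 23 per arm and 12% at 19.

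**3. What that does to the ARAT comparison.** This depends on r, the correlation of baseline Fugl-Meyer with gain, which the documents do not give. If pre and post SDs are equal, a pre-post correlation ρ implies |r| = sqrt[(1 - ρ)/2] between a scale's own baseline and its gain: 0.16 for the ARAT (ρ = 0.95) and 0.21 for the Fugl-Meyer (ρ = 0.91). The values 0.30 and 0.50 are assumptions.

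- Shift in the gain difference from a 0.5 SD imbalance = 0.5 x r x 5.48.
- Conditional power at 19 per arm, if the imbalance is adverse, uses d = 0.84 - 0.5r.
- Adjustment replaces the SD by SD x sqrt(1 - r²), at the cost of one degree of freedom.

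| r | Shift (points, of 4.6 planned) | Conditional power, adverse 0.5 SD | Power with adjustment, 19 per arm | n per arm for 80% with adjustment |
|---|---|---|---|---|
| 0.16 | 0.44 | 0.74 | 0.823 | 18 |
| 0.30 | 0.82 | 0.67 | 0.845 | 17 |
| 0.50 | 1.37 | 0.56 | 0.901 | 14 |

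An imbalance in the other direction raises conditional power. These figures use the plan's own one-tailed 0.05, before any Bonferroni correction.

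**4. Fugl-Meyer.** At the plan's effect size of 1.9, the same 0.5 SD imbalance shifts the planned 4.53-point difference by 0.2 to 0.6 points, and conditional power stays near 1.

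**5. Type I error.** Averaged over randomisations, the simulated one-sided error of the unadjusted test is 0.050. Stratifying without adjusting makes the test conservative: 0.035 if the moderate class gains 5 points more (assumption).

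**The case against.** The strongest reply is that random assignment is already valid. The unadjusted test holds its level, gains already remove the baseline level, and the pilot correlations imply an |r| of only about 0.2. All of that stands, and it limits the point to precision and to the single allocation that will be realised. It does not remove the point: ARAT power is close to 0.80, and even r = 0.16 with an adverse 0.5 SD imbalance brings it to 0.74.

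Four stronger readings are tempting, and the documents do not support them.

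- *That the plan says impairment determines response.* It lists potential predictors, home use among them, for a secondary analysis resting on one earlier study.
- *That a definite shift in the Fugl-Meyer result can be computed by giving moderate subjects a fixed extra gain in both arms.* No such gap is stated, and the cited finding concerns robotic therapy only. If it applies in one arm, the shift is about half. A 4-point gap, with 25% of subjects at 30 or above, would alone give an SD of 4 x sqrt(0.25 x 0.75) = 1.7, more than the whole control-arm gain SD of 1.67.
- *That stratifying would enlarge the severity groups for the responder analysis.* Recruitment sets those numbers.
- *That the total score is already available at screening.* Criterion 3 needs one item only.

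A fair objection to the remedy is that baseline adjustment alone would meet most of the concern. That is right, and it is the fallback below. A second is that a stratum of 30 or above merges moderate with mild subjects. That also stands, but at the pilot's intake level few would exceed 50.

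**Conclusion.** The point holds as a matter of precision and robustness. The plan names baseline impairment as a potential predictor, measures it, and uses it neither in assignment nor in the Hypothesis III tests. A mean baseline difference of 5 points or more would arise in about 9-18% of simple 1:1 allocations, against about 1-2% with two strata, under the two assumed baseline distributions. The practical exposure is mainly on the ARAT: power is 0.815 as planned and 0.82-0.90 with adjustment for r from 0.16 to 0.50. The benefit is small at the lower end and material at 0.30 to 0.50. For the Fugl-Meyer, the effect on power is negligible at the plan's own effect size. The MAL cannot be assessed, because the plan has no pilot data on it. A reader might infer that the trial would be biased or its error rate inflated; neither follows. The absence of a stratification scheme is judged on the available text, which includes the design and analysis sections but not everything between sections 6 and 9.

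**What to change.** 1. In section 5 (Overview and Clinical evaluations), state that the full pre-training Fugl-Meyer is completed before assignment.
2. Randomise 1:1 within two strata of that total score, below 30 and 30 or above, using permuted blocks of varying size. This cut also places a score of exactly 30, which the plan's classes leave unassigned.
3. In Data analysis, include the stratum or baseline Fugl-Meyer in the Hypothesis III model and in the between-group comparisons of gains. If baseline Fugl-Meyer is used, enter it by class or with a non-linear term, because the cited pattern peaks at moderate impairment. Do not stratify without adjusting.
4. If assignment has already begun, make the baseline adjustment alone, and specify it before outcomes by group are examined.

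The cost is a two-stratum list, a sentence or two of text and a fixed order of baseline evaluation before assignment. No new measure and no extra subjects are needed. Blocks become slightly more predictable where treatment staff are unblinded, which varying block sizes limit.
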